3.2.3 Study Eye Selection Criteria in Cases of Bilateral Disease

RCD and ESCS usually affect both eyes to a similar degree. In case both eyes of a participant meet the study eye eligibility criteria, the following criteria will be used to select the study eye:

- The eye with more intraretinal fluid will be selected as the study eye;

- If both eyes have similar levels of intraretinal fluid, the eye with worse visual acuity will be selected as the study eye;
- If both eyes have the similar levels of intraretinal fluid and visual acuities, the right eye will be selected as the study eye.

4.0 STUDY DESIGN AND METHODS

4.1 Study Overview

This is a single-center, prospective, uncontrolled, unmasked pilot Phase I/II study of the safety, tolerability and possible efficacy of IFN gamma-1b in participants with RCD and ESCS and macular cystic changes. Initially, one eye of two RCD participants with macular cystic changes and one eye of two ESCS participants with macular cystic changes will receive topical IFN gamma-1b. Enrollment will be halted and the Serious Adverse Event Review Committee will conduct a preliminary assessment of safety and efficacy after two participants in each disease category have completed the 8-week visit. If the committee approves study continuation, three additional participants with RCD and three participants with ESCS will be enrolled. All participants receiving IP will be followed for 52 weeks (one year). During the first study visit, participants receiving IP will be provided with on-campus lodging to evaluate and monitor the participants (baseline, Days 1 and 2). The visits at Weeks 2, 5, 8 and 52 will be outpatient visits. The study will be completed once the final participant has received 52 weeks of follow-up.

4.2 Recruitment

Participants may enroll in this study after referral by a medical practitioner in the private sector, or by another clinic, hospital or medical institution. Participants may enroll in this study concurrently with another NEI or NIH protocol that does not offer ocular treatment with an investigational product, or following completion of another study. Self-referral is permitted. Participants enrolled or previously enrolled in other active NEI protocols may be contacted. If any recruitment materials are used, IRB-approval will be obtained prior to distribution. It is expected that recruitment will be complete within a 12-month period.

4.3 Screening

Screening may be performed using the *NEI Screening Study for the Evaluation and Diagnosis of Potential Research Participants* (08-EI-0102) or the *NEI Evaluation and Treatment Protocol for Potential Research Participants with Ocular Diseases* (08-EI-0169). Participants may also enter this protocol while enrolled in another study or after exiting another. Participants will undergo a standardized medical ophthalmic history, family history and a comprehensive standard-of-care ophthalmologic examination for their disease. Female participants of childbearing potential (see Appendix 5) will undergo a pregnancy test. Positive pregnancy test results from female minors will be shared with both the legal guardian(s) and the minor. Participants who are sexually active will be referred to the NIH gynecologist consult service to discuss appropriate contraception methods prior to completing any study procedures or dispensing investigational product. Consent will be obtained before any study procedures are performed. Screening procedures may include assessment of visual acuity, visual field, color vision, biomicroscopy and fundus examination, electroretinography (ERG), fundus imaging, and OCT (see Appendix 1). A blood sample for genetic testing of the *NR2E3* gene or of RCD-associated genes may be obtained under other NEI protocols.

4.4 Study Visits

Participants receiving IP will be provided with on-campus lodging for the first three days to complete the baseline assessments and for frequent monitoring to ensure good compliance and correct eye drop instillation technique (Days 1, 2 and 3). Scheduled clinic visits will occur at baseline, Days 1, 2 and 3, and Weeks 2, 5 and 8. A 52-week (one year) safety visit may be conducted at the NIH (on site) or with a local ophthalmologist (if the participant is unable/unwilling to come to NIH). Although there may be differences in testing among the various private physicians, at a minimum, all participants receiving IP must provide documentation of the assessments noted in Week 52 on the study flowsheet. After the participant signs a release of information with his/her ophthalmologist, the examination results will be sent to NEI. NEI will pay for the costs associated with obtaining medical records.

In addition, one of the investigators will conduct a phone interview with participants receiving IP at Weeks 1 and 6 to inquire about ocular complications. One or more unscheduled visits for safety assessment can be added based on the discretion of the investigators.

The regimen of IFN gamma-1b administration will consist of two weeks of therapy, dosing the study eye four times daily, with each dose consisting of a four-drop series, each drop spaced by 5 minutes, for a total of 16 drops delivered per day. The daily dose of IFN gamma-1b will be 112 µg topically (7 µg per drop, applied in 16 drops). Punctal occlusion will be employed to reduce systemic absorption. Investigators will train participants receiving IP on proper drop administration and monitor participants during the initial visits.

If at any time during the study participants experience ocular redness or other ocular concerns, they will be evaluated as soon as possible and the investigator may choose to terminate or reduce the dosage of the IFN gamma-1b eye drops. The dosage may be reduced to a three-drop series four times daily if symptomatic ocular surface disease and/or red eye develops.

Participants receiving IP may be restarted on the drops if the ocular condition resolves, at the investigator's and participant's discretion. Follow-up visits to manage ocular complications will be arranged, independent of and in addition to the prescribed visit schedule of the protocol.

If the participants agree, a skin biopsy and/or blood samples will be obtained, to develop fibroblast and lymphoblast cell lines that will be used to develop stem cells. Participants will be required to submit a blood sample but they will have the option to provide a skin biopsy. Participants who do not agree to a skin biopsy will *not* be excluded from the protocol.

It is anticipated that participants in this study will occasionally miss or fail to complete an assessment, procedure or study visit. These omissions will be considered expected events and not protocol deviations provided they are infrequent and do not include data needed to assess safety or the primary study outcome. Cumulative proportions of these missed events in the study population will be presented to the IRB annually. In addition, the rate of omissions will be monitored by the Investigators and biannually by the NEI SAE Review Committee. If an individual misses more than 15% of the required investigational product doses, assessments/procedures or study visits (or completes them outside the visit window), or if more

than 15% of the participants miss completion of the same assessment or procedure, it will be considered a deviation and a deviation report will be sent to the IRB within two weeks.

4.4.1 Study Evaluations

The following examinations will be performed at the study visits as indicated in the study flowsheet (Appendix 1). Examinations will be performed both as clinical care and for research purposes.

1. Medical/Ophthalmic History
2. Brief Physical Examination
3. Concomitant Medication Assessment
4. Adverse Event Assessment
5. Vital Signs (weight, blood pressure (BP), respiration, temperature)
6. Best-corrected Visual Acuity (BCVA) using EVA (Appendix 4)
7. Manifest Refraction
8. Slit Lamp Examination
9. Dilated Fundus Examination
10. Intraocular Pressure (IOP)
11. Color Vision Assessment (Cambridge Color Test)
12. Color Fundus Photography (CFP) / Fundus Autofluorescence Imaging (FAF)
13. Lens photography
14. Optical Coherence Tomography (OCT)
15. Fluorescein Angiography (FA)
16. Microperimetry
17. Electroretinography (ERG)
18. Electrooculography (EOG)
19. National Eye Institute Visual Functioning Questionnaire - 25 (VFQ – 25) (Appendix 3)
20. Serum Chemistry Panels (Acute Care and Hepatic)
21. Serum Chemistry to obtain IFN gamma levels and antibody titers
22. Complete Blood Count (CBC) with differential

23. Pregnancy Testing

24. Skin Biopsy and blood sample to derive iPSCs*

- a. A 3 mm skin biopsy may be collected. The same procedure will be used for adults and children. **Participants who do not agree to a skin biopsy will **not** be excluded.*
- b. Thirty (30) mL of blood may be collected by phlebotomy to derive iPSCs. For children, no more than the lesser of 5 mL/kg or 30 mL of blood will be collected.

4.5 Study and Concomitant Therapies

4.5.1 Product Overview

IFN gamma-1b, (Actimmune[®], Horizon Pharma), a biologic response modifier, is a single chain polypeptide containing 140 amino acids. Actimmune[®] is a highly purified sterile solution consisting of non-covalent dimers of two identical 16,465 dalton monomers.

Actimmune[®] is a sterile, clear, colorless solution. Each 50 microliters (µL) of solution contains 10 µg (200,000 IU) of IFN gamma-1b with 2 mg mannitol, 14 µg succinic acid, 37 µg of disodium succinate hexahydrate and 5 µg of polysorbate 20 in sterile water for injection. This solution has a pH of approximately 5.2 and an osmolality of 221 mmol/kg.

4.5.2 Investigational New Drug (IND) Requirement

The study will be conducted under IND 105,631.

4.5.3 Preparation and Administration

Commercially-available Actimmune[®], manufactured by Horizon Pharma, will be used in this study and provided to the NIH CC Pharmacy. Vials of Actimmune[®] will be placed in a 2-8° C (36-46° F) refrigerator immediately upon receipt to ensure optimal retention of physical and biochemical integrity. The vials will not be frozen. Excessive or vigorous agitation will be avoided and the vials will not be shaken. The vials will be shipped from the NIH CC Pharmacy under controlled conditions to Pine Pharmaceuticals ([name]) to be re-packaged into single daily use 1 mL dropper bottles. IFN gamma-1b will be supplied to participants in the re-packaged single daily-use dropperettes to be stored in a 2-8° C (36-46° F) refrigerator. A single dropperette contains 1 mL of IFN gamma-1b (Actimmune[®]) at a

concentration of 200 µg/mL, which is equivalent to 28 drops. Each drop provides a dose of 7 µg of investigational product. Between daily uses, participants will store the open dropperette in the refrigerator or in a cooler with a cold pack at 2-8° C. Participants will be given cooler bags for transporting dropperettes. Once opened, each dropperette should be discarded within 24 hours. Participants will be given containers for disposal of the used dropperettes.

Participants will use a new dropperette each day as instructed from the Day 1 visit through the day prior to the Week 2 visit (see Appendix 2). Administration of topical IFN gamma-1b drops should be spaced throughout the day (approximately at breakfast, lunch, dinner and bedtime depending upon the dosage received) as instructed. Participants will be instructed to immediately discard dropperettes after each day's use in the provided disposal container which will be returned to the clinic at their next visit. Participants will be instructed on the proper administration techniques during their initial visit.

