3.0 PARTICIPANTS

Up to five participants with RCD with significant macular cystic changes and up to five participants with ESCS with significant macular cystic changes will be enrolled to receive topical IFN gamma-1b in one eye. However, up to an additional two participants may be enrolled in order to obtain the five participants in each disease group to be included in the primary analysis if any participants withdraw from the study prior to receiving five days of treatment.

The inclusion and exclusion criteria are outlined in the following sections.

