4.5.4 Drug Accountability

The NIH CC Pharmacy is responsible for the accountability of all unused investigational product. Adequate drug accountability records include documentation of all investigational products and supplies shipped, received, prepared and dispensed by the NIH CC Pharmacy. Participants will be asked to complete an eye drop diary documenting the number of drops as well as the days and times the investigational product was administered. At each applicable visit, participants will return the eye drop diary, unused investigational product and used investigational product dropperettes in the disposal container. The investigator/study staff will review the eye drop diary with the participant for completeness and accuracy and document the number of returned dropperettes (both used and unused). Missed doses of investigational product and incorrect doses below the prescribed amount will be documented in the eye drop diary but will not be reported to the IRB as protocol deviations. The study staff will dispose of returned investigational product dropperettes in the hazardous waste disposal bins.

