7.0 OUTCOME MEASURES

7.1 Primary Outcome Measures

The primary outcome measure related to the safety and tolerability of IFN gamma-1b administered topically at the prescribed dosage for macular cystic changes in participants with RCD and ESCS will be assessed by the number and severity of adverse events related to the IP and the number of withdrawals.

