8.1 Analysis

All reported adverse events will be tabulated and presented by system organ class, severity and relationship to study therapy.

Secondary outcomes will be presented for each participant and tabulated over time, as described in Section 7.2. Additionally, these outcomes will compare the changes within the study eye from baseline and the changes between the study eye and control eye over time.

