APPENDIX 1: STUDY FLOWSHEET

Visit Schedule	Baseline	Day 1	Day 2	Day 3	Week 1	Week 2	Week 5	Week 6	Week 8	Week 52
Visit Number	000	000A	000B	000C	001	002	005	006	008	SFTY ⁸
Target Day from Baseline	0	1	2	3	7	14	35	42	56	365
Visit Window					±1 day	±5 days	±7 days	±7 days	±7 days	±30 days
Investigational Product										
Interferon Gamma-1b Dropperettes Dispensed		X ¹	X ¹	X ¹						
Drug Accountability Review						X				
General Assessments										
Medical/Ophthalmic History	X									
Brief Physical Examination	X									
Concomitant Medications Assessment	X	X	X	X		X	X		X	X
Adverse Event Assessment	X	X	X	X		X	X		X	X
Vital Signs	X	X	X			X			X	
Telephone Assessment					X			X		
Ophthalmic Assessments										
BCVA (EVA)	X	X	X	X		X	X		X	X
Manifest Refraction ²	X								X	
Slit Lamp Examination	X	X	X	X		X	X		X	X
Dilated Fundus Examination	X	X	X	X		X	X		X	X
Intraocular Pressure (IOP)	X	X	X	X		X	X		X	X
Color Vision Assessment (Cambridge Color Test)	X ³						X			
Color Fundus Photography (CFP)	X ³					X			X	
Fundus Autofluorescence (FAF)	X ³					X			X	
Lens Photography	X ³					X			X	
Optical Coherence Tomography (OCT)	X ⁴	X ⁴	X ⁴	X ⁴		X	X		X	
Fluorescein Angiogram (FA)	X ³					X				
Microperimetry	X ³		X				X		X	
Electroretinography (ERG)	X						X			
Electrooculography (EOG)	X		X			X	X		X	
NEI VFQ-25	X ³					X			X	
Research Sample Collection										
Skin Biopsy for iPSCs ⁵		X								
Blood Sample for iPSCs ⁵		X								

Visit Schedule	Baseline	Day 1	Day 2	Day 3	Week 1	Week 2	Week 5	Week 6	Week 8	Week 52
Visit Number	000	000A	000B	000C	001	002	005	006	008	SFTY ⁸
Laboratory Testing										
CBC with differential	X ³					X			X	
Chemistry Panels (Acute Care and Hepatic)	X ³					X			X	
Serum IFN gamma levels and antibody titers ⁶	X		X			X				
Pregnancy Testing ⁷	X						X		X	

- ¹ Investigational product may be instilled by clinic staff during the first three days of IP administration and will be prescribed as necessary to maintain the dosing regimen.
- ² BCVA with manifest refraction must be performed when scheduled and when there is a change in EVA of >10 E-ETDRS letters (> 0.20 logMAR) as compared with relevant baseline.
- ³ These procedures can be completed under NEI protocols 08-EI-0102 or 08-EI-0169 if performed within 9 days prior to Visit 000.
- ⁴ This test will be performed at least once but can be performed up to three times daily to assess for acute/subacute changes in macular cysts.

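### The stop rule for dosing follows the Week 2 visit date, so as written it does not deliver the stated two-week course: 13 days on target, 8 at the earliest permitted visit

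*Combined protocol and SAP*

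**What the plan says.** Section 4.4 sets the length of the course: "The regimen of IFN gamma-1b administration will consist of two weeks of therapy". It also sets the daily amount at 16 drops of 7 µg, or 112 µg.

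Section 4.5.3 sets the first and last dosing days. Participants open a new dropperette "each day as instructed from the Day 1 visit through the day prior to the Week 2 visit (see Appendix 2").

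The flowsheet in Appendix 1 places the Week 2 visit at Day 14 with a window of ±5 days, that is, Days 9 to 19. It marks dispensing on Days 1 to 3 only, and its first footnote says that product "will be prescribed as necessary to maintain the dosing regimen". No number of dropperettes is given in the text available.

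Section 4.5.4 has participants bring back the diary and any unused product at visits where this applies. The flowsheet marks drug accountability at Week 2 only. The diary holds the exposure record: "Participants will be asked to complete an eye drop diary documenting the number of drops as well as the days and times" of use.

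On analysis, Section 8.1 states: "All reported adverse events will be tabulated and presented by system organ class, severity and relationship to study therapy". It plans no listing of exposure.

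**The concern.** The length of treatment should be a property of the regimen. Here the operative instruction makes it a by-product of scheduling. An early visit inside the window complies with the protocol, yet it shortens the course, and nothing in the visible text makes up the missing days. Return of unused product at the visit points against dosing afterwards.

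This matters because the primary outcome is the "safety and tolerability of IFN gamma-1b administered topically at the prescribed dosage", judged in up to five participants per disease. At that size each participant's exposure carries weight. Section 3.0 allows replacement only "if any participants withdraw from the study prior to receiving five days of treatment", so someone whose drops stopped after 8 days because of a visit date still counts as one of the five. Week 2 OCT, fluorescein angiography and serum interferon and antibody measurements would then follow courses of different length in different participants. Without an exposure listing, a reader could not set the adverse events beside the drug actually received.

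**Working it through.** **Inputs.** Daily dose: 16 drops × 7 µg = 112 µg, which reproduces the figure in Section 4.4. Stated course: two weeks = 14 days. First dosing day: Day 1 (4.5.3). Last dosing day: the day before the Week 2 visit (4.5.3). Week 2 visit: Day 14 ± 5 (Appendix 1). Assumption: all 16 drops are taken on every dosing day, including Day 1.

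**Reference.** 14 days × 112 µg = 1568 µg.

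**Formula.** For a Week 2 visit on Day d, dosing days = (d − 1) − 1 + 1 = d − 1, and cumulative dose = 112 × (d − 1) µg.

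| Week 2 visit | Dosing days | Cumulative µg | % of 1568 µg |
|---|---|---|---|
| Day 9 (earliest permitted) | 8 | 896 | 57% |
| Day 12 | 11 | 1232 | 79% |
| Day 14 (target) | 13 | 1456 | 93% |
| Day 15 | 14 | 1568 | 100% |
| Day 16 | 15 | 1680 | 107% |
| Day 19 (latest permitted) | 18* | 2016* | 129%* |

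*Only if 4.5.3 is followed over the two weeks in 4.4 and enough dropperettes were supplied. The first condition also applies to the Day 16 row.

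The stated 14 days is therefore reached only by a visit on Day 15, one day after target. The documents do not say how visits will scatter. If they fall within 2 days of target (an assumption), the range is 11 to 15 days, or 79% to 107%.

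**Time off drug at Week 2.** Current rule: d − (d − 1) = 1 day for every participant. With the last dose fixed on Day 14 and a visit window of Day 15 to Day 15 + w, it is 1 to 1 + w days: 1 to 3 days for w = 2, and 1 to 6 days for w = 5.

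**Time off drug at Week 5 (Day 35 ± 7, Days 28 to 42).**
- Literal 4.5.3 rule, last dose Day 8 to Day 18: 28 − 18 = 10 to 42 − 8 = 34 days, a spread of 24.
- 4.5.3 rule capped at Day 14 by 4.4: 28 − 14 = 14 to 34 days, a spread of 20.
- Last dose fixed on Day 14: 14 to 42 − 14 = 28 days, a spread of 14.

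Week 8 (Day 56 ± 7) gives the same three spreads.

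**The case against.** The best reply is that Section 4.4 is the regimen and Section 4.5.3 only describes it for a visit that happens on time. The flowsheet footnote about maintaining the regimen fits that reading. The sentence in 4.5.3 also sends the reader to Appendix 2, the medication instruction sheet, which is the likeliest place for a day count. That appendix was not available to this review, so its silence cannot be assumed. What stands: Appendix 2 may settle the matter in practice. What does not: neither 4.4 nor the footnote overrides an explicit last dosing day, and even an on-target visit gives 13 days, not 14.

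A second reply is that Day 9 and Day 19 are the edges of a window, and nothing suggests that visits will cluster there. That is right.

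A third is that the protocol tolerates variable exposure: the investigator may stop, restart or lower treatment ("The dosage may be reduced to a three-drop series four times daily"), and 8 days exceeds the five-day replacement threshold. In 4.4 the word dosage is also used for drops per series, so a short course need not breach the primary outcome's wording. This weakens any charge of inconsistency with Section 7.1. It does not explain why exposure should vary with the appointment date.

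Last, the current rule has a real merit. Every Week 2 assessment falls exactly one day after the last dose, and fixing the stop day gives that up.

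**Conclusion.** As written, the visible stop rule does not deliver the stated course. The shortfall is one day on target and up to six days at the permitted early limit; the overrun to 18 days is conditional. Because Section 8.0 plans descriptive analysis without hypothesis tests, the consequence is uneven exposure behind the safety and OCT results. Severity is minor to moderate, with moderate confidence. The conclusion rests on a literal reading of 4.5.3, full daily dosing, and no contrary day count in Appendix 2. If that appendix fixes 14 days, what remains is to reconcile the wording of 4.5.3 and add the exposure listing.

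A reader might infer more than this, and the documents do not support it:

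- **That an early visit gives less drug than the permitted dose reduction.** Reduced dosing is 3 × 4 × 7 = 84 µg a day, and 14 days of it is 1176 µg, above 896 µg. But that assumes reduction from Day 1, whereas 4.4 allows it when symptoms develop, and it applies a different stop rule to each side. Under the same 8-day stop, reduced dosing gives 672 µg, below 896 µg.
- **That a fixed course settles the 15% missed-dose rule in 4.4.** It would give a denominator of 14 × 4 = 56 doses, but 4.5.4 says that missed doses are not reported to the IRB as deviations, and a day count does not resolve that.
- **That fixing the stop day cuts the spread in time off drug at Weeks 5 and 8 from 24 to 14 days.** The 24 depends on the conditional 18-day course. If 4.4 caps dosing at Day 14, the starting spread is 20. The remaining 14 comes from the ±7-day visit windows.

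**What to change.** State in Sections 4.4 and 4.5.3 that dosing runs from Day 1 through Day 14 regardless of the visit date, one dropperette a day and 14 in all, and make Appendix 2 agree. In the flowsheet, set the Week 2 visit no earlier than Day 15, with a forward-only window. Its width is for the sponsor to choose: once the stop day is fixed, the width no longer affects exposure, only the days off drug at Week 2. Add to Section 8.1 a listing, from the existing diary, of each participant's dosing days and cumulative µg, including any reduction or interruption, beside the adverse events.

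The cost is a short amendment and one listing from data already collected. Early Week 2 visits are no longer allowed, which may inconvenience participants who travel. A window of 0 to +2 days would leave 3 permitted days in place of 11; a wider one restores flexibility. Week 2 imaging and serum samples no longer fall a constant one day after the last dose, so the listing should also show that interval.
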